16. Any relevant medical, surgical, or psychiatric condition, laboratory value, or concomitant medication which, in the opinion of the Investigator, makes the subject unsuitable for study entry or potentially unable to complete all aspects of the study.
17. Subject has severe or moderate renal impairment (creatinine clearance <50 mL/min) or on dialysis.
18. Subject has moderate (Child-Pugh categorization B, score 7-9) or severe (Child-Pugh categorization C, score 10-15) hepatic impairment ( Lucey MR, 1997).

19. Subject has a lifetime history of suicide attempt (including an active attempt, interrupted attempt or aborted attempt), or has suicidal ideation in the past 6 months as indicated by a positive response ('Yes') to either Question 4 or Question 5 of the Columbia-Suicide Severity Rating Scale (CSSRS) at Screening.
20. Subject has known hypersensitivity or intolerance to pramipexole or rasagiline or to any components or excipients of the test drug or placebo.
21. Subject who has a history of neuroleptic malignant syndrome.
22. Subject who is pregnant or breastfeeding.
23. Subject, who, for any reason, is judged by the Investigator or the EMC to be inappropriate for this study, including a subject who is unable to communicate or cooperate with the Investigator or who has/had a clinically significant illness or abnormal physical examination that may compromise safety of the subject during the trial or affect ability of the subject to adhere to study procedures.

A site will not be allowed to randomize subjects unless their diagnosis and suitability for the study has been confirmed and documented by both the Investigator and the EMC and they are deemed to be a satisfactory candidate by the EMC.

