### **8.3.9 Suicidality**

Columbia Suicide Severity Rating Scale (CSSRS, see Appendix VIII) will be used. Baseline / screening version of the CSSRS will be used at screening visit. This version assesses suicidality in a patient's lifetime and during the past six months. The Since Last Visit (SLV) version of the CSSRS will be used at all consequent visits. This version assesses suicidality since the patient's last visit. Efforts must be made to ensure that the same trained team member completes this questionnaire for each subject.

A subject with any suicidal ideation that answered YES to questions 4 or 5 in the CSSRS questionnaire will be referred to a mental health professional.

CSSRS-SLV will be used on the baseline visit and at end of weeks 3, 5, 8, 12/Treatment Termination visit and end of week 14 (visits 3, 4, 5, 6 and 7).

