After completion of all the testing for the assessment of eligibility, it will be decided by the Investigator whether the subject is eligible for the study. For a subject to be eligible all the inclusion criteria must be met and none of the exclusion criteria must apply. Therefore, all the results from the screening procedures must be available before determining a subject's eligibility. Subjects found eligible will be further reviewed by a central eligibility monitoring committee (see 16.4.2). The maximal interval between the screening and baseline visits is 28 days that can be extended up to 35 days, however, additional Sponsor approval will be required. Extension beyond 35 days and up to 90 days may be approved but will require a new collection of screening laboratory samples at an unscheduled visit prior to baseline. Subjects that are screen failures may rescreen for the study. If the rescreening visit is within 28 days (or 35 days with sponsor approval) of the original blood testing, the screening number remains the same and the blood draw does not need to be repeated, unless it is the reason for the screening failure. Subjects complying with inclusion/exclusion criteria will be randomly assigned to one of the four treatment groups by a central website-based computer program using Randomization Trial Supply Management (RTSM). A randomization form must be completed via the RTSM as soon as possible after subject eligibility was confirmed in order to trigger shipment of investigational product for this subject.

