### **9.2.3 Visit 2 - Baseline**

The time between visit 1 (screening), and visit 2 (baseline), will be no less than 24 hours and no more than 28 days (or up to 90 days with sponsor approval). In this visit a medication kit will be dispensed to him/her together with a leaflet of instructions for use. The subject will be given an emergency contact card with 24-hour contact numbers. The subject will be instructed to keep the contact card with him/her at all times.

The following activities will be performed:

- Dispensation of study medication kit
- Vital signs (HR, BP RR and temperature), weight and ECG
- Urine pregnancy test for women of childbearing potential
- Concomitant medications
- Adverse events review
- Inclusion/Exclusion criteria review
- Study drug dispensing and dosing instructions

- UPDRS II and III questionnaire
- CSSRS- SLV questionnaire
- CGI-S questionnaire
- PDQ39 questionnaire
- ESS questionnaire
- QUIP-RS questionnaire
- HRQOL SF-12v2
- Orthostatic hypotension scale question 1 for subjects with OH

The treatment should be started according to the dosing instructions the day after the baseline visit.

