### **15.9 Columbia Suicide Severity Rating Scale (CSSRS)**

The Columbia Suicide Severity Rating Scale Screening/Baseline Version (CSSRS-BL) will be taken at screening. The Columbia Suicide Severity Rating Scale Since Last Visit (CSSRS-SLV) was to be taken at baseline and in all subsequent study visits.

Any positive answer to its behavior subcomponents at screening or baseline will identify a subject as with “Suicidal Behavior at Baseline”. Similarly, any positive answer to it’s the ideation subcomponents at any of these two visits will identify a subject as with “Suicidal Ideation at Baseline”. A subject identified with either “Suicidal Behavior at Baseline” or with “Suicidal Ideation at Baseline” was also classified as with “Suicidal Behavior or Ideation at Baseline”. Similarly, any positive answer to its behavior subcomponents in any of the post-dosing visits will identify a subject as with “Suicidal Behavior Post Dosing”. Similarly, any positive answer to it’s the ideation subcomponents in any of the post-randomization visits will identify a subject as with “Suicidal Ideation Post Dosing”. A subject identified with either “Suicidal Behavior Post Dosing” or with “Suicidal Ideation Post Dosing” was also classified as with “Suicidal Behavior or Ideation Post Dosing”.

The distribution of the number of subjects by these classifications post-dosing as well as shift analysis from baseline will be displayed. In addition, for the CSSRS-SLV, listing of Post First Study Dose CSSRS (Ideation) Grade 4 and 5 / Suicidal Behavior will be provided.

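### Section 15.9 counts post-dosing suicidal ideation from randomization rather than from first dose, so ideation found at the pre-dose baseline visit also enters the post-dosing category

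*Protocol*

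**What the plan says.** Section 15.9 of the protocol sorts subjects into baseline and post-dosing categories, separately for behavior and ideation, and then into a combined category for either.

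- Ideation at baseline uses screening and the baseline visit: a positive answer to the "ideation subcomponents at any of these two visits will identify a subject as with" ideation at baseline.
- Behavior post dosing: "any positive answer to its behavior subcomponents in any of the post-dosing visits will identify a subject as with" post-dosing behavior.
- Ideation post dosing: a positive answer to the "ideation subcomponents in any of the post-randomization visits will identify a subject as with" post-dosing ideation.

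The planned output is the distribution of the post-dosing categories, a shift analysis from baseline, and a listing of grade 4 and 5 ideation and suicidal behavior. The listing is limited to the period after the first study dose.

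Three other places fix the order of events.

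- CSSRS: section 15.9 states that the since-last-visit version "was to be taken at baseline and in all subsequent study visits". Section 8.3.9 agrees: "CSSRS-SLV will be used on the baseline visit and at end of weeks 3, 5, 8, 12/Treatment Termination visit and end of week 14".
- Randomization: section 9.2.2 states that "A randomization form must be completed via the RTSM as soon as possible after subject eligibility was confirmed", and gives shipment of the subject's drug as the reason.
- First dose: section 9.2.3 states that "The treatment should be started according to the dosing instructions the day after the baseline visit".

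**The concern.** Two definitions that should run in parallel start from different events. That would be harmless if no CSSRS were taken between randomization and first dose, but the baseline visit falls in exactly that interval. The answers given there describe the period since screening, before any study drug. Section 15.9 already assigns them to the baseline category, and the ideation rule assigns them to the post-dosing category as well.

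Suicidality is a named safety objective (section 4.4), and the post-dosing distribution and shift table are its planned summaries. At stake are a post-dosing ideation count that may include pre-dose reports, a combined category that merges components observed over different periods, and a shift table that can hide resolution of ideation after baseline.

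**Working it through.** The plan states no figure on this point, so the check is to order the events and apply the definitions literally.

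**Order of events**

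1. Screening (Visit 1): the baseline version of the CSSRS is completed.
2. Randomization: on approval by the investigator and the eligibility committee, as early as possible so that the kit can be shipped (sections 9.2.2 and 12.2; Appendix I).
3. Baseline (Visit 2): the kit is dispensed (sections 9.2.3 and 12.3), so the subject must already be randomized. The since-last-visit CSSRS is completed, covering the interval from screening, which is at least 24 hours and normally at most 28 days (up to 90 with sponsor approval, section 9.2.3).
4. First dose: the day after Visit 2.
5. Visits 3 to 7: the since-last-visit CSSRS at weeks 3, 5, 8, 12 and 14.

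Visit 2 is thus the one scheduled CSSRS visit that is both post-randomization and pre-dose.

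**Classification of a treated subject, by when ideation is reported**

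| Ideation reported at | At baseline | Post dosing, as written | Post dosing, dose-based | Shift, as written | Shift, dose-based |
|---|---|---|---|---|---|
| No visit | No | No | No | No to no | No to no |
| Screening only | Yes | No | No | Yes to no | Yes to no |
| Visit 2, no later visit | Yes | **Yes** | **No** | **Yes to yes** | **Yes to no** |
| Visit 2 and a later visit | Yes | Yes | Yes | Yes to yes | Yes to yes |
| Visit 3 or later only | No | Yes | Yes | No to yes | No to yes |

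Only the third row differs. It follows that:

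- Post-dosing ideation count as written = dose-based count + number of subjects with ideation at Visit 2 and at no later visit.
- The combined behavior-or-ideation count rises by at most the same number. A subject in that row who also has post-dosing behavior is already counted.
- The no-to-yes cell is identical under both rules, because every subject in the third row is positive at baseline.
- A subject with suicidal behavior only at Visit 2 is counted at baseline only, since the behavior rule uses post-dosing visits.

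**Comparison with the plan's other safety rules**

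Treatment-emergent adverse events start at or after first administration (section 15.7.1). Potentially clinically significant laboratory and vital-sign values are likewise taken from after first administration (sections 15.7.2 and 15.7.3). The CSSRS listing within section 15.9 is also limited to after first dose. The ideation rule is the exception.

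**The case against.** The strongest reply is that this is a drafting slip that no careful programmer would follow. The category is labelled post dosing, the ideation sentence is introduced as parallel to the behavior sentence, the reporting paragraph speaks of post-dosing classifications, and screening and baseline have already been given to the baseline category. That reading is probably what was intended. It makes the correction uncontroversial, but it does not remove the conflict: one programmer may follow the label and another the stated rule, and their counts would differ.

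The limits on the consequences also stand. The most serious outcomes are protected, because the behavior category and the grade 4 and 5 listing both exclude Visit 2. Answers given before dosing cannot be caused by the assigned drug, so with randomization and blinding any inflation is expected to be similar in rate across arms.

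Several stronger readings may tempt a reader, and the documents do not support them.

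- *Pre-treatment ideation would appear as new ideation attributable to study drug.* It would not: the affected subjects are positive at baseline and cannot enter the no-to-yes cell.
- *These events would be reported as occurring on treatment.* The protocol's label is post dosing, and that period includes the off-drug week 14 visit.
- *A definite number of subjects is misclassified.* Any such number needs an assumed rate of ideation at Visit 2. Multiplying that rate by 525 would in any case give an upper bound, because subjects with later ideation belong in the post-dosing count.
- *Exclusion 19 has the same defect, because it refers* "to either Question 4 or Question 5 of the Columbia-Suicide Severity Rating Scale (CSSRS) at Screening". Naming screening is a stated choice about eligibility, separate from the analysis rule, and exclusions 16 and 23 still apply at the Visit 2 eligibility review.

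**Conclusion.** The ideation rule in section 15.9 is wrong as written. It places ideation reported at Visit 2, before any dose, in the post-dosing ideation category and therefore in the combined category. The effect is confined to subjects with ideation at Visit 2 and at no later visit: each adds one to the post-dosing ideation count, at most one to the combined count, and moves from yes-to-no to yes-to-yes in the shift table. How many there would be cannot be derived from the documents.

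The conclusion rests on a literal reading of section 15.9 and on randomization preceding Visit 2, which the drug-supply sequence requires. One point cannot be settled. The SAP takes precedence over the protocol (section 15.13), but version 2.0 is not among the documents. Only its addendum is, and that deals with the modified intention-to-treat set and does not mention the CSSRS. The full SAP may already have corrected the rule.

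**What to change.** In section 15.9, and in SAP version 2.0 if it repeats the wording, define post-dosing ideation from post-dosing visits instead of post-randomization visits, and state that this means visits after the first study drug intake. Ideation, behavior, the combined category and the listing then share one starting point, and Visit 2 belongs to baseline only.

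The cost is a one-word replacement plus a short clarification, and a check that the table and shift programs use the first-dose date. No new data, visits or analyses are needed.

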#### **15.10 Tolerability Assessments**

Tolerability analysis will be based on the number (%) of subjects who discontinued the study treatment early and the number (%) of subjects who discontinued study treatment early due to adverse events. Time to withdrawal will be presented by Kaplan-Meier curves.

#### **15.11 Exploratory Safety Endpoint**

Exploratory comparison between P2B001 0.6/0.75 mg and Pramipexole ER at Week 12/Treatment Termination will be performed in the following safety endpoints:

- Change from baseline to Week 12/Treatment Termination in the ESS score > 10.
- Adverse event frequency
- Change from baseline to Week 12/Treatment Termination in the differences in systolic and diastolic blood pressure measured during supine and standing positions.
- Comparison of percentage of patients presenting with sleepiness/drowsiness related AE’s.
- Comparison of percentage of patients presenting with gastrointestinal (GI) adverse events.
- Comparison of percentage of patients presenting with neurological adverse events.
- Change from baseline to Week 12/Treatment Termination visit in the Orthostatic Hypotension Symptoms Assessment (OHSA) question 1.

#### **15.12 Safety assessment scales**

Results of scale assessments of daytime sleepiness, suicidality, and impulse control behaviors will be presented by study group

#### **15.13 Statistical Analysis Plan (SAP)**

A more detailed SAP will be developed while the study is ongoing and prior to locking the database and unblinding.

If ever there is a discrepancy between the Protocol and the Statistical Analysis Plan, the methods defined in the SAP will have precedence.

## **16 STUDY PERSONNEL**

### **16.1 Study Site**

At each study center the staff will consist of a minimum of one Principal Investigator and a clinical coordinator. If the Principal Investigator at a study center is not a neurologist, then the study center will need at least one sub-Investigator who is a neurologist. The neurologist will: Verify subject eligibility (including diagnosis of early PD and UPDRS part III) at Visits 1 and 2 Perform complete physical and neurological examinations at Visit 1 and symptom-directed physical and neurological examination at visit 7 and unscheduled visits.

The neurologist will also decide on the dose of Pramipexole ER (or matching placebo) during the titration phase based on subject reporting of efficacy and tolerability. This will be done by a study visit at the end of week 3, and a phone call or an unscheduled visit at the end of week 4. The Pramipexole ER (or matching placebo) dose will be evaluated again at the end of week 5 as part of the activities done in study visit 4.

Assess Clinical Global Impression- Severity at Visits 2 and 6.

Assess Clinical Global Impression- Improvement at Visits 4, 5 and 6.

Perform UPDRS part III at Visits 1, 2, 4, 5 and 6 or the Site PI may delegate this responsibility to other senior trained research staff with at least 10 years' experience in conducting the UPDRS All other study procedures can be conducted by the Principal Investigator, Clinical Coordinator or other member of the clinical staff with the relevant experience and who the PI has delegated to perform those procedures.

#### **16.1.1 The Principal Investigator**

The Principal Investigator (PI) will have overall responsibility to lead the site study team and all aspects of the study. The PI will oversee the accrual of appropriate subjects, the conduct of the study according to the trial protocol, communication with the IRB/EC, and the collection of required data.

#### **16.1.2 The Clinical Coordinator or designee**

The clinical coordinator or designee, as delineated on the Personnel Delegation Log, will be responsible for subject scheduling; completing and reviewing all subjects' case report forms and other documents and recording of adverse events as well as drug accountability. He/she will instruct the subject on proper study drug administration and completion of study scales

(including follow-up phone calls to the subject to obtain missing data from subject efficacy or safety scales completed at the previous visit). He/she will instruct the subject on proper study drug dosing. During the titration phase at the end of Weeks 1, 2 and 6 he/she will make a phone call to the subject to assure proper study dosing in the past week and remind of the dosing regimen for the next week.

He/she will collect and forward blood samples and requests to the appropriate laboratories, will obtain and forward laboratory results and will assist the Investigator.

### **16.3.2 Statistics and Data Management Centers (S&DM)**

The CRO's lead data manger is responsible for data management of electronic CRF's. Statistical analyses will be performed by StatExcellence Ltd., Israel.

### **16.3.3 Medical Monitor**

The Medical Monitor is responsible to periodically review the safety data in a blinded fashion to include AEs, vital signs, ECG and laboratory values. A consistency check of safety and efficacy variables will be performed.

### **16.3.4 Local Clinical Trial Manager (LCTM)**

The LCTM based at CRO subsidiaries, is responsible for the local day-to-day activities of the study and to ensure that the sponsor supplies adequate resources to provide high quality study management, monitoring and data management. The LCTM is responsible for submitting all safety reports to local regulatory authorities and to Investigators, as required. The LCTM supervises the monitoring activities.

### **16.3.5 Clinical Research Associate**

Clinical Research Associate (CRA, monitor) is responsible for monitoring visits. These visits will be arranged in advance, at a mutually acceptable time, with site personnel. Sufficient time

must be allowed by the site personnel for the Monitor to review the relevant source documents. The coordinator and/or Investigator(s) should be available to answer questions or resolve data clarifications. Adequate time and space for these visits should be made available by the Investigator. The monitor will review, on a regular basis, the progress of the study with the Investigator and other site personnel and check completeness and blind maintenance. The monitor will verify the data entered into the eCRF for accuracy and completeness. At the end of the study, a close-out monitoring visit will be performed.

## **16.4 Study Committees**

### **16.4.1 Data & Safety Monitoring Board (DSMB)**

The DSMB is intended to assist and consult on any safety aspects to ensure the safety of study subjects. Pharma Two B with the study CRO (PRA Health Science) will be responsible to select DSMB members among different experts in the field. The committee will review, periodically, in unblinded fashion, all safety data accumulated in the study. The committee will document all their recommendations which will be provided to the sponsor and the CRO.

### **16.4.2 Subject Central Eligibility Monitoring Committee (EMC)**

After the Investigator has determined a subject has met all of the inclusion criteria and none of the exclusion criteria but before randomizing the subject via RTSM, the Investigator will need to complete a randomization authorization form (RAF) for that subject and e-mail it to the EMC, which consists of expert Parkinson's disease neurologists. Upon receipt of the RAF, the EMC will review the provided information to confirm the subject's eligibility for the study. Only after receiving confirmation from the EMC that the subject meets eligibility criteria via a signed RAF, may the Investigator randomize the subject using the RTSM system. The EMC may also reject the inclusion of a subject due to that subject not meeting eligibility criteria. Any rejection will be explained to the Investigator via email.

## **17 REGULATORY AND ETHICAL ISSUES**

### **17.1 Compliance with Regulations Applicable to Clinical Trials**

The study will be conducted according to the protocol, the laws, regulations and administrative provisions relating to the implementation of GCP in the conduct of clinical trials on medicinal products for human use, as applicable by national legislation and directives, including Directive 2001/20/EC of the European Parliament and the Council of the European Union and US 21 CFR Part 11, 50, 54, 56 and 312.

### **17.2 Informed Consent**

The principles of informed consent, according to Declaration of Helsinki 1964 and all its updates, the International Conference on Harmonization (ICH) step 5 guidelines on Good Clinical Practice (GCP), 21 CFR part 50 of the FDA Regulations and/or EU Directives, will be followed. A subject should not enter a clinical study or perform any study-related procedures until subject has been properly informed, has been given time to contemplate participation, and has freely given his/her consent by signing and dating the EC/IRB approved informed consent form.

The proposed consent form and any other documents relevant to the consent process must be submitted to the EC/IRB together with the protocol and must be approved prior to study start. A signed copy of the consent form will be given to the subject and the original will be maintained at the site following the signing and dating by the person administering the consent and witness (where appropriate).

